End-of-trial form														X	X		

- a) Screening will be performed up to 4 weeks before the baseline visit. If the screening visit is performed close to the beginning of the washout period, no additional washout phone call is necessary, at the discretion of the investigator.
- b) Subjects who permanently discontinue IMP treatment prior to week 4 will be asked to return to the trial site for a primary endpoint (nominal week 4) visit.
- c) An end-of-treatment form must be completed in the eCRF for all randomised subjects.
- d) An end-of-trial form must be completed in the eCRF for all randomised subjects.
- e) Subjects who permanently discontinue IMP prior to week 16 and subjects who withdraw from the trial will be asked to come to an early termination visit. As an early termination visit will only be performed in case of subjects permanently discontinuing the IMP, the visit has been marked with an (X).
- f) Unscheduled visit(s) between planned visits may be added to the subject's visit schedule if judged necessary by the investigator, e.g. due to an AE, a significant change in disease state, or difficulty complying with the clinical trial protocol requirements. At an unscheduled visit, the investigator should at least collect AEs

Version: 5.0

- data. Other assessments/procedures to be conducted at an unscheduled visit will be at the discretion of the investigator. As unscheduled visits will only be performed if judged necessary by the investigator, the assessments/procedures have been marked with an (X).
- g) The informed consent form must be signed prior to performing any protocol-related procedures, including but not limited to screening evaluations and washout of disallowed medications.
- h) In case medical history is incomplete at the screening visit because prior and concomitant diseases were not communicated by patient before or e.g. in case of abnormal lab values from screening assessments, missing data will be documented at week 0 (baseline).
- i) Mycobacterium tuberculosis IFN-γ release assay (or a PPD test if it is a requirement from the local health authorities).
- j) For women of childbearing potential
- k) Preparation, administration and handling of IMPs will only be performed by unblinded site staff
- l) All subjects must use an emollient twice daily (or more frequently, if needed) for at least 7 days before day 1 (baseline) and throughout the treatment period (until week 16).

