#### Safety follow-up period (week 17 to week 32)

In the safety follow-up period, the subject will not receive any treatment with LEO 138559 or comparator injections. The safety of the subject will further be assessed at 3 safety follow-up phone calls (weeks 20, 24, and 28) and at a final safety follow-up visit at week 32. Topical treatment for AD will be permissible during the safety follow-up period. At the end of trial visit the diary will be collected and assessments will be conducted as specified in Panel 2.

Subjects who require treatment with other biologics will prematurely discontinue the trial.

Subjects who discontinue the trial early should be requested to return for an early termination / end of trial visit (see also Section 10.3) at the time of the decision to withdraw from the study.

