### 10 Discontinuation and withdrawal

## 10.1 General principles

A subject may withdraw from the trial (prior to first dose or during the treatment period) or permanently discontinue trial treatment at any time if the subject, the investigator, or LEO Pharma considers that it is not in the subject's best interest to continue.

A subject who withdraws from the trial is a subject who stops treatment with the IMP and all further protocol defined trial activities. A subject who permanently discontinues IMP is a subject who, although they stop treatment with the IMP, agree to their follow-up as described in Section 10.3. Early termination assessments to be conducted for both events are described in Section 10.3.

If a subject withdraws from the trial, they may request destruction of any samples taken and not tested. The investigator must document this in the subject's medical record and inform LEO Pharma.

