#### Withdrawal from trial

Subjects who withdraw from the trial after first dose of IMP for any reason will be asked to attend an early termination visit as soon as possible after last administration of IMP (see the schedule of trial procedures [Section 4] for data to be collected at an early termination visit). The investigator will review any AEs which will be followed up according to Section 13.7, if the subject agrees.

Details on data to be recorded in the eCRF for subjects who withdraw from the trial can be found in Section 11.8.

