# 13.2 Collection of adverse event reports

AE data must be collected from time of first trial-related activity after the subject has signed the informed consent form (ICF) until subject's completion of the clinical trial (safety follow-up visit at week 32 see Section 7.3)

AEs must be assessed by a physician.

At all visits, the subject will be asked a non-leading question by the investigator about AEs, e.g.: "How have you felt since I saw you last?" No specific symptoms should be asked for. It is important that the investigator also observes the subject for any changes not reported by the subject and records these changes.

Principles for data entry in the eCRF are described in Sections 11.4.1 to 11.4.5

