## 14.3.6 Secondary endpoint analysis

The secondary endpoint

• Number of treatment-emergent adverse events from baseline to week 16 per subject

will be analysed descriptively on the safety analysis set by computing the number of treatment-emergent adverse events per subject by treatment group.

Trial ID: LP0145-2274 Date: **04-Jan-2023** Version: 5.0 Page 96 of 129

An event will be considered treatment-emergent if started after the first dose of IMP or if started before the first dose of IMP and worsened in severity after first dose of IMP. An event will not be considered treatment-emergent if starting 18 weeks after the last dose of IMP.

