#### 14.3.9.1 Adverse events

AEs will be coded during the course of the trial according to Medical Dictionary for Regulatory Activities (MedDRA). AEs will be presented by preferred term and primary system organ class (SOC).

Treatment-emergent AEs will be summarised; however, all AEs recorded during the course of the trial will be included in subject data listings. The tabulations described in the following will only include the treatment-emergent AEs. In each of the tabulations, AEs are defined by MedDRA preferred terms within primary SOC.

AEs will be summarised in terms of the number of subjects with at least 1 event, the percentage of subjects with at least 1 event, the number of events, and the event rate per 100 patient years of observation time.

Related AEs are defined as AEs for which the investigator has not described the causal relationship to IMP as 'not related'.

An overall summary of the number of events and the number (percentage) of subjects with any treatment-emergent AEs, deaths, SAEs, permanent discontinuations from IMP, and/or withdrawals from the trial due to AEs, treatment-related AEs, mild and moderate AEs, and severe AEs will be presented.

Tabulations by SOC and preferred term will be presented for all AEs, SAEs, related AEs, and AEs leading to withdrawal from trial and/or permanent discontinuation of IMP. In addition, all AEs will be presented by severity and causal relationship to IMP, respectively.

The number of AEs and number of subjects with each type of AEs will be tabulated by treatment group from baseline to week 16, from baseline to week 32, and from week 17 to week 32.

AEs leading to withdrawal from trial and/or permanent discontinuation of IMP will be tabulated and listed. The detailed listing will provide an overview of the individual cases and include the age and sex of the subject, treatment received at the time of AE onset, the AE preferred and reported terms, causality and severity of the AE, the action taken with the IMP, AE outcome, start and stop date of AE, duration of AE, and number of days since first and last IMP administration. No narratives will be given.

SAEs will be evaluated separately, and a narrative will be given.

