#### 14.3.9.5 Anti-drug antibodies

For the exploratory endpoint

• Having a positive ADA response at weeks 0, 4, 8, 12, 16, 32, assessed separately.

the ADA status (positive vs. negative) including actual ADA titre at each assessment time point will be summarised. If considered relevant, descriptive statistics including number of subjects, mean, SD, median, and range of the actual ADA titres and visit will be provided. The ADA status across the trial for each subject (positive vs. negative) will also be classified and summarised.

The association of ADA status across the trial (positive vs. negative) with AEs/SAEs may be evaluated. In addition, the association of ADA titres (≥ median titre in positive subjects versus < median titre) with AEs/SAEs may be evaluated for ADA positive treated subjects only. The ADA positive subjects across the trial may also be divided into persistent positive versus transient positive. A subject will be considered as persistent positive if he/she has positive ADA for at least 2 consecutive visits with ADA assessment. Otherwise, the subject will be considered as transient ADA positive. The associations between ADA and AEs/SAEs may be summarised for both persistent positive subjects versus transient positives subjects.

For subjects who develop ADA, the change in EASI at end of treatment will be listed.

For ADA, all subjects with titre information will be listed. Graphical presentations may be performed.

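### A subject who needs another biologic in weeks 17–32 must leave after one exit visit, which ends active AE follow-up and forfeits the week-32 ADA and laboratory assessments: a minor gap that is cheap to close

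*Combined protocol and SAP*

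**What the plan says.** Section 7.1, in its text on the safety follow-up period, plans telephone calls at weeks 20, 24 and 28 and a visit at week 32. It then states: "Subjects who require treatment with other biologics will prematurely discontinue the trial". Subjects who leave early are asked to one early termination / end of trial visit when the decision is made.

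Section 10.1 defines what leaving means: "A subject who withdraws from the trial is a subject who stops treatment with the IMP and all further protocol defined trial activities". Section 10.3 lists only the exit visit for them: "Subjects who withdraw from the trial after first dose of IMP for any reason will be asked to attend an early termination visit". By contrast, Section 10.3 gives a subject who merely stops IMP a further visit 16 weeks after the last dose.

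AE collection under Section 13.2 runs until the subject's "completion of the clinical trial (safety follow-up visit at week 32 see Section 7.3". Section 14.3.6 closes the treatment-emergent window as follows: "An event will not be considered treatment-emergent if starting 18 weeks after the last dose of IMP". Section 14.3.9.1 tabulates AEs by treatment group "from baseline to week 16, from baseline to week 32, and from week 17 to week 32".

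ADA is an exploratory endpoint at week 32, the only scheduled ADA time point after week 16. Section 14.3.9.5 defines a persistent positive as "positive ADA for at least 2 consecutive visits with ADA assessment".

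**The concern.** The follow-up period exists to observe safety after dosing, and the sponsor's own treatment-emergent window fills it exactly. The exit rule stops active observation inside that window because of a treatment decision, not because the subject refuses further contact. After exit nobody asks about new AEs at the remaining calls, and the week-32 ADA and laboratory results are lost.

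At stake are the week 17–32 and 0–32 AE tables and the week-32 rows for ADA and laboratory values. With 8 and 4 subjects planned per arm, one exit is visible in those tables. Someone who needs another biologic soon after dosing ends may also still carry a material amount of LEO 138559.

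**Working it through.** **Inputs**
- Last dose at week 14 (Sections 7.1 and 9.2).
- Treatment-emergent window of 18 weeks after last dose (Section 14.3.6).
- Follow-up contacts at weeks 20, 24, 28 and 32 (Section 7.1, Panel 2).
- Planned arm sizes of 8 and 4 (Section 7.2).
- Half-life of 21–25 days after multiple dosing (Section 5.2, Pharmacokinetics).

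**Reproducing the plan's window.** 14 + 18 = week 32, and 32 × 7 + 1 = day 225. That is visit 16, so any follow-up exit before that visit falls inside the window.

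**Formulas for an exit visit at week w.** The exit weeks are illustrative; Section 7.1 sets the visit at the time of the decision.
- Contacts lost = those scheduled after week w, out of 4.
- Post-dose weeks unobserved = (32 − w) / 18.
- Share of the arm's week 17–32 person-weeks lost = (32 − w) / (n × 16). The denominators are 8 × 16 = 128 and 4 × 16 = 64.
- Days from last dose to last ADA sample = 7 × (w − 14).
- Share of end-of-dosing level remaining = 2^(−days / half-life).

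| Exit | Contacts lost | Weeks unobserved | LEO 138559 person-weeks | Comparator person-weeks | Last ADA sample | Drug remaining |
|---|---|---|---|---|---|---|
| Week 20 | 3 of 4 | 12/18 = 67% | 12/128 = 9.4% | 12/64 = 18.8% | 42 days | 25–31% |
| Week 24 | 2 of 4 | 8/18 = 44% | 8/128 = 6.3% | 8/64 = 12.5% | 70 days | 10–14% |
| Week 28 | 1 of 4 | 4/18 = 22% | 4/128 = 3.1% | 4/64 = 6.3% | 98 days | 4–7% |

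A completer's last ADA sample falls 7 × 18 = 126 days after last dose. One LEO 138559 exit removes 1 of 8 week-32 ADA results (12.5%).

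The last column assumes linear elimination and dates decline from the last dose. Section 5.2 reports target-mediated disposition, which could lower the later values. The column shows only that earlier exits matter more.

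**Does another section restore the contacts?**
- Section 13.7 continues outcome follow-up of SAEs and of related non-serious AEs after a subject leaves.
- Section 13.4.1 has later SAEs reported if the investigator learns of them.
- Neither provides for asking about new AEs, and neither reinstates the week-32 samples.

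**The case against.** The strongest case against is that the gap is narrow, of unknown frequency and already softened.

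- **Narrow trigger.** Section 7.1 allows topical treatment in follow-up, and Panel 5 allows systemic corticosteroids if medically indicated. No rate of biologic use is given. This stands, so every figure above is per exiting subject.
- **Low consequence.** The trial is exploratory and descriptive, without formal tests. The laboratory shift table uses end of treatment, and the ECG and physical-finding shift tables use week 16. This stands.
- **Disclosure.** Section 14.3.9.1 includes event rates per 100 patient-years. Section 14.3.12 reports how many subjects lack data at each visit. Both reduce the harm. The sentence on the period tables names only counts of events and subjects, and the text does not settle whether rates accompany them. In any case a rate adjusts for lost time but does not recover unobserved events.
- **Attribution.** Events after a new biologic are harder to assign, so stopping there is defensible. This is the real cost of the change. It argues for flagging and censoring more than for ending observation, since systemic corticosteroids are already tolerated in follow-up.
- **Scope.** Section 9.5 still withdraws subjects who need other systemic AD therapy during dosing, and Panel 5 also bars JAK inhibitors to week 32. This is fair, but 9.5 governs the treatment phase, and the forced exit in follow-up is written for biologics only.

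Several stronger readings are tempting, and the documents do not support them:

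- A reader might infer that exit samples are optional because "the visit has been marked with an (X". Panel 2 footnote e explains that the mark means the visit itself is conditional. AE review and ADA, PK and laboratory samples are scheduled there.
- A reader might infer that ADA persistence will be misclassified. A first positive at exit indeed cannot be confirmed, but Section 14.3.9.5 makes the persistent/transient split optional. A completer first positive at week 32 has no later sample either.
- A reader might count the week-32 PK sample as a serious loss. Section 12.1 expects concentrations below quantification in most subjects by 16 weeks after last dose.

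**Conclusion.** The concern holds as a minor point. Sections 7.1, 10.1, 10.3 and 13.2 together end active AE questioning and the week-32 ADA and laboratory assessments for a subject who needs another biologic in follow-up, inside the sponsor's own window. The loss per exit at week 20, 24 or 28 is 12, 8 or 4 of 18 post-dose weeks, plus one week-32 ADA result and one set of laboratory results.

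The person-week percentages assume exactly 8 and 4 subjects. Section 7.2 says approximately 12 will be randomised, so the true shares could be somewhat lower. No expected number of exits can be stated; if nobody exits, nothing is lost.

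A reader might infer a threat to the trial's main conclusions. The documents do not support that: the primary endpoint is read at week 4 and the secondary endpoint stops at week 16, both before the rule applies.

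**What to change.** Amend the safety follow-up text of Section 7.1, and the biologics row of Panel 5 for the follow-up period only:

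- A subject who needs another biologic has safety, ADA, PK and laboratory assessments before its first dose where possible. No skin biopsy is taken and no end-of-trial form is completed at that point.
- The subject then stays in the trial for the remaining safety calls and the week-32 visit.
- The biologic and its start date are recorded, and later AEs and ADA results are flagged.
- The week 17–32 and 0–32 AE tables are shown with all events and again censored at biologic start, each with observation time.
- Section 9.5 stays unchanged, and the text says explicitly that it governs the dosing period.

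The cost is an amendment to two places and a second version of two tables. Per subject it is at most three calls and one visit, all already scheduled. Section 9.7 already requires prohibited treatments to be recorded as concomitant medication. The downside is harder attribution after the biologic starts, which the flag and the censored tables handle.

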### 7.2 Number of subjects needed

This trial will be conducted at one site in Austria. Approximately 12 subjects will be randomised in a 2:1 ratio to LEO 138559 450 mg Q2W (8 subjects) and comparator 300 mg Q2W (4 subjects) to be able to achieve 12 subjects evaluable for the primary endpoint i.e., for whom a lesional biopsy is available at baseline and week 4.

Page 45 of 129

The statistical considerations for this sample size are described in Section 14.1.

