#### **Overall rationale for the amendment:**

A new serum biomarker in atopic dermatitis has been identified in the literature. This amendment is intended to include this new biomarker. In addition, this amendment is intended to clarify that randomization will be continued until 12 patients who are evaluable for the primary endpoint i.e., for whom lesional skin biopsies at baseline and week 4 are available, are included in the study.

Section no.	Description of change	Brief rationale
and name		
11.6.2 Blood	Addition of newly identified	With the identification of a new blood
biomarkers	biomarker IL-22BP to the list of	serum biomarker for atopic dermatitis,
	blood serum biomarkers that	LEO Pharma A/S has decided to add
	will be analysed.	this biomarker to the set of biomarkers
		that will be analysed in this clinical
	Formerly (First paragraph):	trial.
	Evaluation of effects of treatment	
	of AD patients with LEO 138559	
	or Dupixent® on protein	
	biomarkers in blood, including but	
	not limited to E- selectin,	
	PI3/Elafin, CCL7, and IL-16, will	
	be performed on serum samples.	
	New:	
	New:	
	Evaluation of effects of treatment	
	of AD patients with LEO 138559	
	or Dupixent® on protein	
	biomarkers in blood, including but	
	not limited to E-selectin,	
	PI3/Elafin, CCL7, and IL-16, and	
	newly identified IL-22BP [50]	
	will be performed on serum	
	samples	
	Wording regarding the number	Originally a replacement of patients
	of patients to be randomised	was planned if more than 3 patients left
	rephrased:	the study before the end of the 4th week
	- F	of treatment.
		However, it was always the intention to
		achieve 12 subjects evaluable for the
		primary endpoint i.e., for whom a
		lesional biopsy is available at baseline
		and week 4.
		Wording has been revised for clarity.

Date: 04-Jan-2023

Section no.	Description of change	Brief rationale
and name		
	Formerly:	
Protocol	A total of 12 subjects will be	
Synopsis	randomised 2:1 to:	
	• LEO 138559 (8 subjects).	
	• Dupixent® (4 subjects).	
	New:	
	Approximately 12 subjects will be randomised 2:1 to:	
	• LEO 138559 (8 subjects).	
	• Dupixent® (4 subjects).	
	Formerly:	

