## 9.3 Treatment assignment and blinding

## 9.3.1 Treatment assignment

Treatment assignment will be pre-planned according to a computer-generated randomisation schedule. This **randomisation schedule** randomly allocates subjects who have been found to comply with all the inclusion criteria and not to violate any of the exclusion criteria on day 1 (visit 3) in a 2:1 ratio to one of the two treatments, LEO 138559 or comparator. Randomisation envelopes will be provided to the site. The randomisation number has to be documented in the CRF.

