## 14 Statistical methods

# 14.1 Sample size

The sample size of 12 subjects evaluable for the primary endpoint i.e., for whom a lesional biopsy is available at baseline and week 4 (8 receiving LEO 138559 and 4 receiving comparator) is based on the trial design for the exploratory comparison of the molecular signature changes of LEO 138559 and the comparator. The sample size is not based on power calculations.

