## 14.3.5 Primary endpoint analysis

The primary endpoint

 Change in biomarkers in lesional skin biopsies typically associated with atopic dermatitis from baseline to week 4

will be analyzed descriptively by computing the following statistics by treatment group: minimum and maximum value, lower and upper quartile, median, mean, standard deviation and median absolute deviation.

Individual and mean data as well as boxplots will be plotted by treatment group.

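### Does the plan need a same-arm replacement rule to secure the 8 and 4 evaluable subjects given in Section 14.1?

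*Combined protocol and SAP*

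**What the plan says.** Section 7.2 sets the number randomised: "Approximately 12 subjects will be randomised in a 2:1 ratio to LEO 138559 450 mg Q2W (8 subjects" and 4 on comparator. It gives the purpose as "to be able to achieve 12 subjects evaluable for the primary endpoint i.e., for whom a lesional biopsy is available at baseline and week 4", and refers to Section 14.1 for the statistical considerations.

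Section 14.1 attaches the split to the evaluable subjects: "8 receiving LEO 138559 and 4 receiving comparator) is based on the trial design for the exploratory comparison of the molecular signature changes". It adds that the number does not come from a power calculation.

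On allocation, Section 9.3.1 says: "Treatment assignment will be pre-planned according to a computer-generated randomisation schedule". The ratio is 2:1, and "Randomisation envelopes will be provided to the site". It mentions no block size, reserve list or same-arm replacement. Section 10.1 currently has no replacement rule.

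The Amendment 3 rationale gives the intention that "randomization will be continued until 12 patients who are evaluable for the primary endpoint" are included, again as a total.

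Two further places matter. In the schedule of trial procedures (Section 4), footnote b states: "Subjects who permanently discontinue IMP treatment prior to week 4 will be asked to return to the trial site for a primary endpoint" visit at nominal week 4. Section 14.3.5 says the primary endpoint "will be analyzed descriptively by computing the following statistics by treatment group", with individual data plotted by group.

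**The concern.** Section 14.1 gives the evaluable sample by arm, whereas Section 7.2 and the amendment rationale secure only the total. If a comparator subject has no week 4 biopsy, the next envelope is more likely to be LEO 138559 than comparator, and the trial could stop at 9 and 3.

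The comparator arm has only 4 subjects by plan and is the mechanistic reference for LEO 138559 (Section 12.1). Losing one removes a quarter of that arm, and the quartiles, standard deviation and median absolute deviation would then rest on three values. A reader of Section 14.1 would expect four. On its face, a stated per-arm target lacks a rule that delivers it.

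**Working it through.** **Inputs from the documents.** Target of 12 evaluable subjects (Sections 7.2 and 14.1); 2:1 allocation (Sections 7.2 and 9.3.1); stated split of 8 and 4 (Section 14.1); randomisation continued to a total of 12 evaluable (Amendment 3 rationale).

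**Inputs assumed.** The chance p that a subject lacks the baseline and week 4 biopsy pair: 5%, 10% or 20%, equal in both arms and independent between subjects. A 2:1 list in blocks of 3, 6 or 12, with each new subject taking the next place. The documents state neither.

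**Step 1: the plan's own figure.** 12 × 2/3 = 8 and 12 × 1/3 = 4. Section 14.1 reproduces.

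**Step 2: one loss, by hand.** Suppose the first 12 are split 8 and 4, one subject is lost at random, and the next place is LEO 138559 with probability 2/3.

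- Comparator lost, LEO 138559 next (9 and 3): 1/3 × 2/3 = 2/9 = 22%.
- LEO 138559 lost, comparator next (7 and 5): 2/3 × 1/3 = 2/9 = 22%.
- Same arm lost and gained (8 and 4): 1/3 × 1/3 + 2/3 × 2/3 = 5/9 = 56%.

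The harmful outcome has an equally likely mirror image, so the expected comparator count is unchanged: 4 − 2/9 + 2/9 = 4.

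**Step 3: the whole rule, by simulation.** 200,000 lists per setting, continued to 12 evaluable. Ranges run over block sizes 3, 6 and 12.

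| Evaluable comparators | p = 5% | p = 10% | p = 20% |
|---|---|---|---|
| Fewer than 4 | 10.6–10.9% | 17.2–18.5% | 24.4–26.9% |
| of which 2 or fewer | 0.4–0.5% | 1.1–1.7% | 3.1–4.6% |
| Exactly 4 (split 8 and 4) | 78.0–78.5% | 62.9–64.8% | 46.1–50.0% |
| More than 4 | 10.9–11.1% | 18.0–18.6% | 25.6–27.0% |
| Mean count | 4.0 | 4.0 | 4.0 |

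The row for more than 4 is 1 minus the fewer-than-4 and exactly-4 rows within each block size. For blocks of 3 at 10%: 1 − 0.172 − 0.648 = 0.180.

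**Step 4: what continuing to 12 evaluable already buys.** With 8 and 4 randomised and no replacement, P(fewer than 4 comparators) = 1 − (1 − p)^4:

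- p = 5%: 1 − 0.95^4 = 19%
- p = 10%: 1 − 0.90^4 = 34%
- p = 20%: 1 − 0.80^4 = 59%

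Continuing brings these down to about 11%, 17–19% and 24–27%.

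**Step 5: size of the loss when it happens.** In units of the outcome SD, the standard error of a between-arm difference is √(1/8 + 1/4) = 0.612 at 8 and 4, and √(1/9 + 1/3) = 0.667 at 9 and 3, a rise of 9%. The plan calculates no such interval; the figure is only a measure of scale.

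**Step 6: cost of arm-matched replacement.** The expected number randomised is 12/(1 − p) under either rule: 12.6, 13.3 and 15.0. Recruitment is therefore not the cost. The cost falls on concealment: a replacement's arm is known in advance to anyone who knows or guesses the lost subject's arm.

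**The case for a change.** The strongest case for a change is that Section 14.1 states four evaluable comparators, that no supplied text delivers four, and that one sentence would close the gap. It could say the arm sizes are expected to be about 8 and 4, or require replacement in the same arm. The first option is only wording, and the second needs no more subjects on average. With so small a reference arm, a shortfall is not trivial.

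The textual part stands: none of the supplied sections contains a same-arm rule. The case for acting on it is weaker. Section 7.2 refers to Section 14.1, so read together they give 8 and 4 as the planned split under 2:1 allocation, and that split is right on average. Inserting an approximate qualifier leaves every allocation and every result as it was, and Section 7.2 already calls the total approximate. Same-arm replacement would alter the arm sizes, but it gives up some concealment in a double-blind trial run with envelopes at one site. Reasonable statisticians would differ on that exchange.

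Two cautions apply to the probabilities. They depend on blocking: with unblocked 2:1 allocation, fewer than 4 comparators would occur in about 39% of trials even with no missing biopsies, which has nothing to do with replacement. Block size or reserve envelopes may also be set in a randomisation specification that was not supplied. Further, a loss here means a missing biopsy rather than any early stop, because early discontinuers are asked back at nominal week 4. Nothing in the documents points to the upper end of the assumed range.

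**Conclusion.** No change to the plan follows. The 8 and 4 in Section 14.1 is a correct planned split, and what is missing is an operational detail. On the assumptions of a blocked list, equal and independent loss in both arms, and randomisation continued to 12 evaluable, the chance of fewer than 4 evaluable comparators is about 11% at 5% loss, rising to 24–27% at 20%. The usual shortfall is one subject, and it is balanced by a similar chance of a surplus.

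Followed as written, the plan still gives sound results. The sample size has no power basis (Section 14.1), no significance tests are planned (Section 14.3.4), and Section 14.3.5 shows individual values and summaries by group, so the comparator data can be judged as they are. Analysts will report the evaluable numbers actually reached in each arm. Leaving the replacement's arm to the randomisation list is a fair trade-off for keeping allocation unpredictable.
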